7.1.1.3.2 The Alzheimer's Disease Assessment Scale – Cognitive Subscale

The ADAS-Cog/11 ([Rosen 1984](#)) ([Appendix 2](#)) includes 11 items assessing cognitive function ([Skinner 2012](#)). The domains include memory, language, praxis, and orientation. There are 70 possible points, 48 for the first 9 items, and 22 for the last two items, word recall, and recognition. Test performance is assessed for errors in following ordered commands, naming of real objects and of fingers, constructional praxis (copying of geometric forms), ideational praxis (preparation of a letter for mailing), orientation, a 10-item word recall task and a 12-item and 12 foils word recognition task. Higher scores reflect greater cognitive impairment. Individual testing domains may be separated out for the purposes of statistical analysis.

7.1.1.3.3 Grooved Pegboard Test

The Grooved Pegboard Test is a manual dexterity test measuring visual-motor coordination ([Lafayette 2002](#)). The test consists of a pegboard with 25 holes with randomly positioned slots and pegs with a key along one side. The subject is to insert the pegs as quickly as possible into the slots in sequence, first with the dominant hand and then with the non-dominant hand. The score is the time it takes for the subject to complete the task.

7.1.1.3.4 Category Fluency Test

The CFT is one of the validated nine components of the neuropsychological test battery. Category fluency tasks are an important component of neuropsychological assessment, especially when evaluating for dementia syndromes. Subjects are asked to name as many different types of animals, vegetables, and fruits, in that order, as they can in a 60 second period. The number of correct, non-repeated responses for each individual category constitute the raw score for the specific category. The total category fluency score is calculated by adding the number of correct responses for the pooled categories ([Acevedo 2000](#)).

7.1.1.3.5 Clinical Dementia Rating Scale – Sum of Boxes

The Clinical Dementia Rating Scale (CDR) is a global assessment instrument that yields global and sum of boxes (SOB) scores, with the global score regularly used in clinical and research settings to stage dementia severity. The CDR is obtained via semi-structured interviews with patients and informants (e.g. trial partners) to characterize functioning in 6 domains: memory, orientation, judgment and problem solving, community affairs, home and hobbies and personal care ([Hughes 1982](#)). Each domain is rated on a 5-point scale, and the CDR-SOB score is obtained by summing each of the domain box scores. The CDR-SOB is considered a more detailed quantitative general index than the global score and provides more information than the global CDR score in patients with mild dementia ([O'Bryant 2008](#)) ([Appendix 3](#)). Individual testing domains may be separated out for the purposes of statistical analysis.

7.1.1.3.6 Alzheimer's Disease Cooperative Study Group – Activities of Daily Living₂₃

The ADCS-ADL₂₃ assesses the competence of patients with AD in performing basic and instrumental activities of daily living. The ADCS-ADL₂₃ contains 23 items covering physical and mental functioning and independence in self-care. For each activity of daily living (ADL), an informant (e.g., trial partner) is first asked if the patient attempted the activity during the past 4 weeks. If a patient did attempt the ADL, the informant (e.g., trial partner) is asked to choose the single most accurate definition of the patient's level of performance. The scores range from 0 to 78, with higher scores indicating less functional impairment ([Galasko 1997](#)) ([Appendix 4](#)).

7.1.1.3.7 Alzheimer's Disease Cooperative Study – Clinical Global Impression of Change

The ADCS-CGIC is a systematic method for assessing clinically significant change in a clinical trial as viewed by an independent skilled and experienced clinician ([Ferris 1997](#), [Schneider 1997](#)) ([Appendix 5](#)). The ADCS-CGIC focuses on clinicians' observations of change in the subject's cognitive, functional, and behavioral performance since

the beginning of a trial. It relies on both direct examination of the subject and interview of informants (e.g. trial partner).

7.1.1.3.8 Neuropsychiatric Inventory Questionnaire

The NPI-Q evaluates the most frequent neuropsychiatric manifestations of dementia and determines their frequency and intensity ([Kaufer 2000](#)) ([Appendix 6](#)). It is designed to be a self-administered questionnaire completed by informants (e.g. trial partners) about subjects for whom they care. Generally, the NPI-Q is used to evaluate changes in subject behavior that have appeared during a given period.

The NPI-Q comprises 12 domains: delusions, hallucinations, dysphoria, apathy, euphoria, disinhibition, aggressivity and restlessness, irritability, anxiety, aberrant motor behavior, appetite and eating disorders, and nocturnal behavior. Initial responses to each domain question are "Yes" (present) or "No" (absent). If the response to the domain question is "No", the informant goes to the next question. If "Yes", the informant then rates both the severity of the symptoms present within the last month on a 3-point scale and the associated impact of the symptom manifestations on them (i.e., trial partner distress) using a 5-point scale. Thus, the NPI-Q evaluates response to therapy and provides symptom severity and distress ratings for each symptom reported, and total severity and distress scores reflecting the sum of individual domain scores.

7.2 LABORATORY PROCEDURES/EVALUATIONS

7.2.1 CLINICAL LABORATORY EVALUATIONS

Biological samples (e.g. whole blood, serum, urine) will be collected for laboratory evaluations in accordance with the Schedule of Events ([Section 17](#)). Clinical sample processing and laboratory evaluations will be conducted by a central lab's registered and certified Clinical Laboratory Improvement Amendments (CLIA) facilities. STAT laboratory evaluations will be conducted at the clinical site. Refer to the study's laboratory manual for complete information regarding all laboratory evaluations to be performed, sample collection procedures, and related requirements.

The investigator is responsible for determining and documenting if out of range laboratory values are clinically significant or not. All clinically significant values will be recorded as AEs in the CRF and followed until resolution, unless the subject is lost to follow up. Once resolved, the appropriate CRF page(s) will be updated.

7.2.2 OTHER ASSAYS OR PROCEDURES

7.2.2.1 Apolipoprotein E (ApoE) Genotype Testing

ApoE genotype is a known risk factor for AD pathogenesis, with presence of the ApoE ϵ 4 allele carrying increased risk. This risk is further influenced by age, sex, race, and ethnicity. Thus, determining ApoE genotype at baseline will allow for the assessment of possible differential effects of ApoE genotype on safety, treatment efficacy, neuroimaging and other exploratory measures.

7.2.2.2 Positron Emission Tomography (Optional)

Documented PET Scan is optional and not required for inclusion in the study.

Subjects who have had a PET Scan using any radioligand within 12 months of screening will be asked to provide copies of the images and results. The historical scan will be used to estimate the density of beta-amyloid neuritic plaque.

Subjects who meet eligibility criteria and who have not had a PET Scan within 12 months of screening will be given the option of having a PET Scan performed and read by a central reader. The results of the scan will be made available to the subject.

7.2.2.3 Magnetic Resonance Imaging

MRI [3 Tesla (T) preferred but 1.5T will be accepted] will be used to evaluate subjects' eligibility for inclusion in the study and to assess safety (ARIA) at Visit 8. MRI may also be used to compare neural activity and brain atrophy at screening/baseline, after the first series of pulsed doses, and at end of study. During the MRI, the subject will be asked to lie on a narrow bed in a large tunnel while images are captured by the MRI machine. The screening and Visit 8 scans will be interpreted by local radiologists to confirm eligibility and the continued safety of subjects. The MR images may also be analyzed centrally at the end of the study by an outside party.

The MRI exam after dosing on Visit 8 will be used to evaluate subjects for possible ARIA. ARIA are MRI abnormalities, including signal changes thought to represent vasogenic edema and/or microhemorrhages that have been seen in subjects enrolled in clinical trials of experimental amyloid-modifying therapies. [REDACTED]

7.2.2.4 Proteomic and Genetic Biobanking

Blood and plasma will be collected from subjects at multiple timepoints throughout the trial for biobanking. For information regarding the timing and procedures for sample collection and related requirements, refer to the study's laboratory manual and [Section 17 Schedule of Events](#).

Plasma will be analyzed by proteomics using mass spectrometry and targeted approaches to assess the specific signature of proteins in subjects at baseline and to assess the changes in the proteome with repeated GRF6019 infusions. These methodologies will provide a broad overview of the proteins that are present in the plasma sample by assessing 1000-5000 analytes and allow generation of a proteomic signature. From this signature, we hope to identify key proteins that are drivers of cognitive function and/or indicators of disease progression. Blood samples will be retained for analysis of emergent genetic markers of disease. By understanding the composition and function of plasma samples from the trial, we seek to identify the biomarkers relevant to further optimizing treatment in AD. For information regarding future use of stored samples, see [Section 12.5 Future Use of Stored Specimens](#).

7.2.2.5 Cerebrospinal Fluid Biomarker Collection (Optional)

Participation in the cerebrospinal fluid (CSF) biomarker research is optional and not required for inclusion in the study.

The CSF collection procedure, as well as the potential risks and benefits, will be explained to all study participants at participating sites. Subjects who are eligible and consent to participate will undergo two lumbar punctures for CSF collection, the first occurring prior to initial dosing, and the second occurring following final dosing. If a subject withdraws from the study early but is willing to provide the second (final) CSF sample, this can be obtained as long as the subject received at least two infusions of GRF6019. If the subject is currently taking antiplatelet therapy (e.g. clopidogrel, prasugrel, ticagrel), this medication must be withheld for 5 days prior to each lumbar puncture (treatment with aspirin can continue).

The lumbar punctures should be performed by a physician experienced in the procedure and according to the site's standard procedures. Both lumbar punctures should be performed at approximately the same time of day and the time should be recorded. For each lumbar puncture, 12-15 mL of CSF will be collected by gravity (not aspiration).

The first 2 mL should be collected for erythrocyte analysis. The remainder should be collected into a low-protein-binding polypropylene CSF collection tube without additives. The CSF should be kept at room temperature until centrifugation. The centrifugation should occur within 1 hour of collection, and the time documented. The tube should be centrifuged at 2,000 g for 10 minutes. The supernatant will be divided into approximately 10 aliquots of approximately 1 mL each. The aliquots should be pipetted into polypropylene tubes with screw caps and immediately frozen. Each aliquot tube should be at least 75% filled, and the number of aliquots should be adjusted to achieve this (depending on the final CSF volume collected).

CSF aliquots will be thawed and analyzed for specific AD biomarker assessments including [REDACTED]. CSF samples will also be analyzed by proteomics using mass spectrometry and targeted approaches to assess the specific signature of proteins in subjects at baseline and to assess the changes in the proteome with repeated GRF6019 infusions. These methodologies will provide a broad overview of the proteins that are present in the CSF samples and allow generation of a proteomic signature. From this signature, we hope to identify key proteins that are drivers of cognitive function and/or indicators of disease progression. For information regarding future use of stored samples, see [Section 12.5 Future Use of Stored Specimens](#).

7.2.3 SPECIMEN PREPARATION, HANDLING, STORAGE, AND SHIPPING

Refer to the study’s laboratory manual for specimen preparation, handling, storage, and shipping procedures.

7.3 STUDY SCHEDULE

Visit windows (when noted) should be benchmarked relative to Visit 3 for a subject, such that subjects complete the entire study by Day 168 (±7 days). Study visit procedures are listed in the recommended order in which they should be completed.

7.3.1 SCREENING

Visit 1, Screening (Day -28 to -8)

- Informed consent of subject (and/or the subject’s legally authorized representative) and the subject’s trial partner must be obtained prior to any study-related assessments
- Administer the C-SSRS
- Assess for probable AD using NIA-AA criteria including MMSE
- Conduct the MHIS
- Obtain medical history, including medical records to support AD diagnosis if available
- Collect demographic information
- Review subject’s current and prior medications
- Review and provide the subject (and subject’s trial partner) with a list of permitted and prohibited medications
- Collect vital signs, height, and weight
- Perform the physical exam
- Perform 12-Lead ECG
- Collect specimens for the laboratory panel
- Perform transthoracic echocardiogram
- Complete MRI
- Complete PET Imaging (optional)

Note: The Screening Visit may be split to allow for sufficient time to complete all required procedures. AEs and concomitant medications should be collected during split visits, as applicable. Any PET Imaging should be completed after the MRI but before Visit 3. The optional PET scan should only be performed after the subject has met criteria for inclusion in the study.

7.3.2 BASELINE

Visit 2, Baseline (Days -7 to -1)

- Re-review screening assessments for eligibility (e.g., MMSE scores, lab values)
- Review AEs and concomitant medications
- Collect the following:
 - Vital signs
 - Samples for proteomics/epigenetics/biobanking (fasting samples are preferred)
 - Buccal swab for ApoE Genotype testing
- Ensure the subject has had an opportunity to eat a meal prior to commencing cognitive and motor testing
- Perform cognitive and motor testing in the following order unless otherwise specified:
 1. Savonix Full Battery
 2. ADAS-Cog/11
 3. Grooved Pegboard
 4. CFT
 5. CDR-SOB (subject and trial partner)
 6. ADCS-ADL₂₃ (trial partner)
 7. ADCS-CGIC (subject and trial partner)
 8. NPI-Q (trial partner self-administered; may be completed by the trial partner at any available time during the visit)
- Confirm subject eligibility prior to initiating treatment
- In consenting, eligible subjects, perform initial lumbar puncture and obtain CSF samples for optional biomarker research.

Note: The Baseline Visit may be split to allow collection of all required assessments.

7.3.3 RANDOMIZATION

It is recommended that subjects be randomized at the start of Visit 3, prior to receiving their first dose. However, subjects may be randomized at any time after eligibility has been confirmed but prior to receiving their first dose on Visit 3.

Subjects who are randomized but do not receive any dose of the study agent, may be re-screened and randomized if they meet all of the study eligibility requirements.

7.3.4 TREATMENT

There are two inpatient treatment periods scheduled during the trial, each with a total of 5 infusions. It is anticipated that sites will infuse subjects with 5 doses over 5 days. A “grace day” is allowed in the event of unanticipated safety or health concerns during each inpatient treatment period.

Visits 3-7 (Days 1-5) and 11-15 (Days 85*-89):

*Day 85 has a ± 7-day window. Visits 12-16 should follow consecutively.

- Perform the following procedures prior to administering study treatment:
 - Review AEs and concomitant medications
 - Obtain blood and urine samples for comprehensive laboratory panel; fasting samples preferred **(Visits 4, 6, 12, and 14 Only)**
 - Obtain samples for proteomics/epigenetics/biobanking; fasting samples preferred **(Visits 3 and 11 Only)**
 - Obtain i-STAT safety laboratory test samples and assess results before each infusion
 - Perform targeted physical exam (i.e. auscultation of heart and lungs and assessment of peripheral edema)
 - Measure and record the subject’s weight in kilograms
 - Perform 12-lead ECG **(Visit 11 Only)**
 - Ensure the subject has had an opportunity to eat a meal prior to cognitive and motor testing
 - Administer the Savonix Brief Battery
 - Perform ADAS-Cog/11 **(Visit 11 Only)**
 - Collect pre-infusion vital signs
- Administer study treatment and perform safety assessments per the Infusion Administration Manual
- Post-infusion: perform 12-lead ECG **(Visits 7 and 15 Only)**

7.3.5 FOLLOW-UP

Visits 8 and 16 (Day 6 and Day 90 – Last Day of Inpatient Stay):

- Review AEs and concomitant medications
- Collect the following:
 - Vital signs and subject’s weight in kilograms
 - Blood and urine samples for comprehensive laboratory panel (fasting samples preferred)
 - Samples for proteomics/epigenetics/biobanking (fasting samples preferred)
 - i-STAT safety laboratory test samples and assess results before discharge
- Perform targeted physical exam (i.e. auscultation of heart and lungs and assessment of peripheral edema)
- Ensure the subject has had an opportunity to eat a meal prior to cognitive and motor testing
- Perform cognitive assessments in the following order:
 1. C-SSRS
 2. MMSE
 3. Savonix Full Battery
 4. ADAS-Cog/11
- Complete MRI **(Visit 8 + 4 days Only)**
- In consenting, eligible subjects, perform final lumbar puncture (after final dosing) and obtain CSF samples for optional biomarker research **(Visit 16 or within 5 days following)**

Visit 9 (Day 28 ±7 days) and Visit 17 (Day 112 ±7 days)

- Review AEs and concomitant medications
- Collect the following:
 - Vital signs
 - Blood samples for interim safety labs (Note: Subjects randomized prior to August 30, 2018, will not participate in the additional interim safety labs at Visit 9 and Visit 17.)
 - Samples for proteomics/epigenetics/biobanking (fasting samples preferred)
- Ensure the subject has had an opportunity to eat a meal prior to cognitive and motor testing
- Perform cognitive and motor testing in the following order unless otherwise specified:
 1. Savonix Full Battery
 2. ADAS-Cog/11
 3. Grooved Pegboard
 4. CFT
 5. CDR-SOB (subject and trial partner)
 6. ADCS-ADL₂₃ (trial partner)
 7. ADCS-CGIC (subject and trial partner)
 8. NPI-Q (trial partner self-administered; may be completed by the trial partner at any available time during the visit)

Visit 10 (Day 56 ±7 days) and Visit 18 (Day 140 ±7 days)

- Review AEs and concomitant medication
- Collect the following:
 - Vital signs
 - Blood and urine samples for comprehensive laboratory panel (fasting samples preferred)
 - Samples for proteomics/epigenetics/biobanking (fasting samples preferred)
- Ensure the subject has had an opportunity to eat a meal prior to cognitive and motor testing
- Perform cognitive assessments in the following order unless otherwise specified:
 1. Savonix Full Battery
 2. ADCS-ADL₂₃ (trial partner)
 3. NPI-Q (trial partner self-administered; may be completed by the trial partner at any available time during the visit)

7.3.6 FINAL STUDY VISIT

Visit 19, End of Study (Day 168 ±7 days)

- Review AEs and concomitant medication
- Collect the following:
 - Vital signs and subject's weight in kilograms
 - Blood and urine samples for exit laboratory panel (fasting samples preferred)
 - Samples for proteomics/epigenetics/biobanking (fasting samples preferred)
- Perform the physical exam
- Ensure the subject has had an opportunity to eat a meal prior to cognitive and motor testing
- Perform cognitive and motor testing in the following order unless otherwise specified:
 1. MMSE
 2. Savonix Full Battery
 3. ADAS-Cog/11
 4. Grooved Pegboard
 5. CFT
 6. CDR-SOB (subject and trial partner)
 7. ADCS-ADL₂₃ (trial partner)
 8. ADCS-CGIC (subject and trial partner)
 9. NPI-Q (trial partner self-administered; may be completed by the trial partner at any available time during the visit)
- Complete MRI

Note: Visit 19 may be split to allow for sufficient time to complete all required procedures.

7.3.7 EARLY TERMINATION

If a subject has received at least one infusion but is terminated or terminates from the study early, the site should try to perform all assessments scheduled at the End of Study Visit. In addition, if a subject withdraws from the study early but is willing to provide the second (final) CSF sample (and has consented and is eligible to participate in the optional CSF biomarker research), this can be obtained as long as the subject received at least two infusions of GRF6019.

7.3.8 SCHEDULE OF EVENTS TABLE

A tabular summary of all procedures that will be accomplished at each study visit can be found in [Section 17 Schedule of Events](#).

7.4 CONCOMITANT MEDICATIONS, TREATMENTS, AND PROCEDURES

All prescription, over-the-counter, and non-prescription medications (including herbal therapies and supplements) must be documented in the source documents and CRFs. All subjects should be maintained on the same medications at the same dosage and administration for treatment of AD throughout the entire study period, as medically feasible, with no introduction of new chronic therapies. Any changes in medications should be documented with reason for change (e.g., adverse event, etc.).

7.5 PROHIBITED MEDICATIONS, TREATMENTS, AND PROCEDURES

The following are prohibited:

- Concurrent participation in another therapeutic treatment trial for AD. If there was prior clinical trial participation, then the last dose of the investigational agent for symptomatic therapies must have been at least 30 days (or 5 half-lives whichever is longer), 4 months for disease modifying therapies, and 1 year for vaccine or immunotherapy trials prior to screening.
- Concurrent daily treatment with benzodiazepines, long-acting opioids, or other medications that, in the investigator’s opinion, interfere with cognition. [Note: intermittent treatment with low-doses of shorter half-life benzodiazepines (e.g. lorazepam, alprazolam) may be permitted, provided that no dose is administered within the 72 hours preceding any cognitive assessment].
- Any anticoagulant therapy; antiplatelet drugs (e.g., aspirin or clopidogrel) are acceptable.
- Any drugs of the interferon class.
- Systemic steroids (e.g., hydrocortisone, cortisone, betamethasone, prednisone, prednisolone, triamcinolone, dexamethasone, fludrocortisone) for longer than 5 consecutive days; ophthalmic, topical, intra-articular and inhaled steroids are allowed.

8 ASSESSMENT OF SAFETY

Assessment of safety will be conducted by blinded study personnel except in extraordinary circumstances where knowledge of the dose received by a subject is essential. Any instances of unblinding will be managed as indicated in [Section 10.6.3 Breaking the Study Blind/Participant Code](#).

8.1 SPECIFICATION OF SAFETY PARAMETERS

8.1.1 DEFINITION OF ADVERSE EVENTS (AE)

Per 21 CFR 312.32(a) an AE is any untoward (unfavorable, harmful, or pathologic) medical occurrence in a subject administered a medicinal (investigational) product even if the event does not necessarily have a causal relationship with this treatment.

An AE can therefore be any unfavorable and unintended sign (including an abnormal laboratory finding that is deemed clinically significant), symptom, or disease temporally associated with the use of a medicinal (investigational) product whether or not related to the medicinal (investigational) product.

An AE does include any:

- Exacerbation of a pre-existing illness
- Subjective or objective symptoms spontaneously offered by the subject and/or observed by the investigator or study staff
- Increase in frequency or intensity of a pre-existing episodic event or condition

- Condition detected or diagnosed after study drug administration even though it may have been present prior to the start of the study (unless it can be demonstrated by medical record review that the onset of the event preceded the date/time of Informed Consent)
- Continuous persistent disease or symptoms present at baseline that worsen following the start of the study
- Symptoms associated with disease not previously reported by the subject
- Lack of efficacy in the acute treatment of a life-threatening disease
- Untoward medical occurrences considered by the investigator to be related to study-mandated procedures
- Abnormal assessments (e.g., change on physical examination, ECG findings), if they represent a clinically significant finding, that were not present at Baseline or worsened during the course of the study
- Laboratory test abnormalities, if they represent a clinically significant finding, symptomatic or not, which were not present at Baseline or worsened during the course of the study

An AE DOES NOT include a/an:

- Elective medical or surgical procedure (e.g., surgery, endoscopy, tooth extraction, transfusion)
- Pre-existing diseases or conditions present or detected at the start of the study that do not worsen
- Situations where an untoward medical occurrence has not occurred (e.g., hospitalization for cosmetic elective surgery, social and/or convenience admissions)
- The disease or disorder being studied or sign or symptom associated with the disease or disorder unless more severe than expected for the subject's condition
- Overdose of either study drug or concurrent medication without any signs or symptoms.
- Symptoms associated with AD that are consistent with the subject's usual clinical course unless the symptom(s) meet(s) the criteria for "serious"
- Pregnancy

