4.2 STUDY ENDPOINTS

4.2.1 PRIMARY ENDPOINTS

The primary endpoints in this study pertain to the safety, tolerability and feasibility of each dose level.

Safety endpoints are as follows:

- Incidence of treatment-emergent adverse events (AEs) identified by MedDRA preferred term (PT) and grouped by MedDRA System Organ Class (SOC).

Tolerability endpoints are as follows:

- Number of subjects completing 8 weeks (i.e. through Visit 10) after receiving at least 5 infusions.
- Number of subjects completing 24 weeks (i.e. through End of Study) after receiving at least 10 infusions.

Feasibility endpoints are as follows:

- Number of subjects completing 5 and 10 infusions.

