8.1.2 DEFINITION OF SERIOUS ADVERSE EVENTS (SAE)

An SAE is any AE occurring at any dose that results in any of the following outcomes (note that if either the investigator or the Sponsor believes that the event is serious, the event must be considered serious and evaluated for expedited reporting). Note that the terms "severe" and "serious" are not synonymous. Severity (or intensity) refers to the grade of an AE. "Serious" is a regulatory definition. A serious adverse event (experience) or reaction is an untoward medical occurrence that, at any dose, fulfills one or more of the following criteria:

- a. Results in death (i.e., the AE actually causes or leads to death)
- b. Is life-threatening
 - An AE is considered "life-threatening" if, in the view of either the investigator or Sponsor, its occurrence places the patient or subject at immediate risk of death; it does not include AEs which, had it occurred in a more severe form, might have caused death
- c. Results in inpatient hospitalization or prolongation of existing hospitalization.
 - Hospitalization for elective treatment of a pre-existing condition that did not worsen during the study is not considered an AE

- Complications that occur during hospitalization are AEs; if a complication prolongs hospitalization, the event is an SAE
 - “Inpatient” hospitalization means the subject has been formally admitted to a hospital for medical reasons that may or may not be overnight; it does not include presentation at a casualty or emergency room unless the event meets the definition of an Important Medical Event (in the opinion of the Investigator or Sponsor)
- d. Results in persistent or significant incapacity or substantial disruption of the ability to conduct normal life functions
- The term ‘disability’ means a substantial disruption of a person’s ability to conduct normal life functions; this definition is not intended to include experiences of relatively minor medical significance such as uncomplicated headache, nausea, vomiting, diarrhea, influenza, accidental trauma (i.e., sprained ankle) that may interfere or prevent everyday life functions but do not constitute a substantial disruption
- e. Results in a congenital anomaly in the offspring of a subject who received drug

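### Two exclusion bullets in Protocol 8.1.1 give opposite answers for a serious Alzheimer symptom of expected severity, and no rule says which one governs

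*Protocol*

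**What the plan says.** Protocol 8.1.1 defines an AE through an include list and an exclude list.

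Three include bullets can reach disease symptoms: "Exacerbation of a pre-existing illness", "Continuous persistent disease or symptoms present at baseline that worsen following the start of the study" and "Symptoms associated with disease not previously reported by the subject". None of them names AD or makes an exception for it.

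Two exclude bullets deal with AD:

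- The studied-disease bullet removes "The disease or disorder being studied or sign or symptom associated with the disease or disorder unless more severe than expected", and ties that expectation to the condition of the individual subject.
- The AD bullet removes AD symptoms that follow the subject's "usual clinical course unless the symptom(s) meet(s) the criteria for" seriousness.

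Protocol 8.1.2 opens with "An SAE is any AE occurring at any dose that results in any of the following outcomes". It also warns that severity and seriousness are separate concepts. Later in the same paragraph it describes a serious event as an untoward medical occurrence that meets a listed criterion, and it lets either the investigator or the sponsor make an event serious.

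TEAE incidence by preferred term and system organ class is the primary safety endpoint (Protocol 4.2.1). SAP 6.1.2 builds TEAEs from the AEs that were reported, and SAP 6.1.5 tabulates serious TEAEs. Neither section restates or settles the rule for AD symptoms.

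**The concern.** Both exclude bullets cover signs or symptoms of AD, but each has its own exception and neither is ranked above the other. A site that applies the studied-disease bullet asks whether the symptom is worse than expected for this subject. A site that applies the AD bullet asks whether it is serious. For a symptom that is serious but of expected severity, the two questions lead to different records.

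Three things start from that classification:

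- the serious-TEAE rows and tables in SAP 6.1.5;
- the 24-hour submission of the SAE form in Protocol 8.4.2.1;
- the first trigger in Protocol 8.5, three or more related SAEs in one system organ class.

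The loss is hard to repair. Protocol 8.4.1 requires AEs to be entered on the AE case report form. An event that a site has ruled out as an AE has no required place there, so data review before lock may never see it. Such events are foreseeable, because Protocol 5.2 generally allows psychosis, irritability or depression arising in the context of AD at entry.

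**Working it through.** The plan has no figure to reproduce here, so the check is a cross-classification of the text.

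**Step 1. Inputs.** The two exclude bullets in Protocol 8.1.1, the include list in the same section, and the definitions in 8.1.2. I treat expected severity for the subject and consistency with the subject's usual course as one factor (expected: yes or no), and seriousness under 8.1.2 as the other.

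**Step 2. Apply each bullet to a new or worsened AD symptom.**

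| Expected? | Serious? | Include list | Studied-disease bullet | AD bullet |
|---|---|---|---|---|
| Yes | No | AE | Excluded | Excluded |
| Yes | Yes | AE | Excluded | Not excluded |
| No | No | AE | Not excluded | Not excluded |
| No | Yes | AE | Not excluded | Not excluded |

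The two exclude bullets disagree only in the second row. Symptoms more severe than expected are AEs under every rule. In the first row the two bullets agree with each other and differ only from the include list.

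**Step 3. Can the second row be settled from the text?** Reading the exclude list as a carve-out from the include list settles the first row. It does not settle the second, because the conflict there lies inside the carve-out. Treating the two exceptions as equivalent is ruled out by 8.1.2, which separates severity from seriousness. No section states an order of precedence.

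**Step 4. Consequence for SAEs.** Under the opening words of 8.1.2 an event must be an AE before it can be an SAE. Applied literally, the studied-disease bullet stops the event before the seriousness criteria are read. The AD bullet reads those criteria first.

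**Step 5. Size.** With 20 subjects per dose group (Protocol 10.5), one reclassified subject moves a group's incidence by 1/20 = 5 percentage points.

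The documents give no rate for serious but expected AD symptoms, so the following is illustration only. Assume a per-subject rate q over the study, independent across 40 dosed subjects. The chance that at least one such event arises is 1 − (1 − q)^40:

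- q = 2%: 1 − 0.98^40 = 0.55
- q = 5%: 1 − 0.95^40 = 0.87
- q = 10%: 1 − 0.90^40 = 0.99

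At the same rates the binomial chance of three or more affected subjects among 40 is 0.05, 0.32 and 0.78. These are not probabilities of meeting the 8.5 trigger, which also requires the same system organ class, a related assessment by the investigator and confirmation by the sponsor.

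**The case against.** A reader might infer something stronger: that 8.1.1 both includes and excludes every new or worsened AD symptom, so that the primary TEAE counts as a whole depend on which bullet a site applies. The documents do not support that. No include bullet names the disease under study, while the exclude bullets address it directly, and the ordinary reading is a general list with a specific carve-out. Both exclusions are also tied to the individual subject. Agitation that is new for a subject is not readily part of that subject's usual course, so it is arguably an AE under the exclusions too. What remains is that no precedence is written down.

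A reader might also infer that an event removed by the studied-disease bullet can never be reported as an SAE. That goes too far. The untoward-occurrence wording in 8.1.2 and its either-party rule on seriousness both point towards reporting. So does the AD bullet, which is the more specific of the two. These protect capture in part, but they help only if the site raises the event.

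Other points on that side have weight:

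- Many serious symptoms will be judged more severe than expected, and then the bullets agree. That makes the conflict less frequent but does not remove it.
- An event seen as the subject's usual course may be rated unrelated and never count towards the 8.5 trigger. Section 8.5 also has a pattern-based trigger that needs no SAE count, and either trigger only convenes a meeting.
- The NPI-Q and the cognitive and global scales record behaviour and cognition outside AE reporting. The cover is partial. The NPI-Q is not scheduled at inpatient Visits 3–8 or 11–16. Efficacy tables use the Evaluable and Per Protocol sets, and SAP section 5 leaves early-termination results out of them.
- Outcomes assessors are blinded, so differing site practice cannot knowingly follow dose. With up to 10 sites and randomisation stratified by sex only, chance imbalance is possible, but nothing shows a direction.

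**Conclusion.** The point holds for one class of event. A serious AD symptom of expected severity is excluded from the AE definition by one bullet in 8.1.1 and not excluded by another, and neither document ranks them. The serious-TEAE tables, 24-hour reporting and the SAE-based trigger in 8.5 all start from that classification.

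The effect is 5 percentage points of a dose group's incidence per subject reclassified. How many subjects that would be is unknown, because the probabilities above rest on assumed rates. The conclusion depends on reading each bullet as written and on 8.1.2's own distinction between severity and seriousness. It does not extend to non-serious expected symptoms, where the carve-out reading is adequate though unstated, nor to symptoms more severe than expected, which are AEs on any reading.

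**What to change.** Merge the two exclude bullets into one that keeps both exceptions, for example: *AD signs and symptoms in line with the subject's usual course are not AEs unless they exceed the severity expected for that subject or meet any seriousness criterion in 8.1.2.* Add that, for AD symptoms, this bullet takes precedence over the include list. A cross-reference in SAP 6.1 would keep the two documents aligned.

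The cost is a sentence or two in 8.1.1 and a short note to sites. The downside is that a few more serious AD-related events are recorded as AEs.

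A broader option is to record every new or worsened AD symptom as an AE, with a yes/no field for consistency with disease progression, and to show the TEAE tables with and without flagged events. This is a trade-off and is not needed to resolve the contradiction. It would turn expected decline over 24 weeks into TEAEs, overlap with the cognitive endpoints and add to many SAP tables.
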